### 8.6.3. Overdose

An overdose is a significant variation from the recommended/scheduled dosage for a product. For this trial, an overdose of setmelanotide is considered a dose higher than:

- 2 mg in any patient
- 1.5 mg in patients with body weight [REDACTED]
- 1.0 mg in patients with body weight [REDACTED]
- 0.5 mg in patients with body weight [REDACTED]

### 8.6.4. Recording Adverse Events

AEs spontaneously reported by the patient/caregiver and/or in response to an open question from the trial personnel or revealed by observation will be recorded during the trial at the investigational site.

Clinically significant changes in laboratory values, BP, and pulse need not be reported as AEs. However, abnormal values that constitute an SAE or lead to discontinuation of administration of trial drug must be reported and recorded as an AE.

AEs will be recorded from obtaining consent until the end of the trial. SAE information will be collected from obtaining consent until EOS. The AE term should be reported in standard medical terminology when possible. For each AE, the Investigator will evaluate and report the onset (date and time), resolution (date and time), intensity, causality, action taken, serious outcome (if applicable), and whether or not it caused the patient to discontinue the trial.

Intensity will be assessed according to the following scale:

- Mild (awareness of sign or symptom, but easily tolerated)
- Moderate (discomfort sufficient to cause interference with normal activities)
- Severe (incapacitating, with inability to perform normal activities)

It is important to distinguish between serious and severe AEs. A severe AE may not be considered serious.

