#### 3.2. Setmelanotide

Setmelanotide is a synthetic, cyclic octapeptide (8-amino acid-containing peptide) that functions as a potent MC4R agonist. Setmelanotide binds with high affinity (inhibitory constant = 2.1 nM) to the human MC4R and is efficient in activating MC4R (50% effective concentration = 0.27 nM). While not an analog, it retains the specificity and functionality of the naturally occurring POMC-derived neuropeptide,  $\alpha$ -MSH, which is the endogenous ligand for the MC4R. Setmelanotide is more potent and has a much longer half-life (~10-12 hours in humans) than the short-lived  $\alpha$ -MSH ligand.

The setmelanotide peptide was initially selected for clinical development based on its acceptable circulating half-life as a saline formulation (2.8 - 3.5 hours in non-human primates) and the ability to decrease body weight gain and suppress food intake in normal rats. Pre-clinical studies demonstrated the efficacy of setmelanotide in suppressing food intake and body weight gain in diet-induced obese mice, rats, dogs, and monkeys, as well as in genetic models of obesity, including leptin-deficient ob/ob mice and leptin receptor deficient obese Zucker rats. Later

[figure not shown]
studies in obese monkeys showed that setmelanotide did not increase blood pressure (BP) or heart rate (HR), a potential concern observed with other MC4R agonist compounds.

To support clinical trials, the toxicological profile of setmelanotide formulations has been evaluated in repeat-dose continuous SC infusion toxicity studies up to 13 weeks in duration in rats and monkeys. The formulation used in almost all of these studies, including the pivotal 28-day and 13-week toxicology studies, was setmelanotide in 0.9% sodium chloride for injection (setmelanotide-saline formulation), tested over a range of concentrations. An International Council for Harmonisation (ICH)-compliant battery of in vitro and in vivo genetic toxicity studies that included a bacterial mutation assay, a chromosomal aberration assay in cultured human peripheral blood lymphocytes and a rat micronucleus study has been completed with this formulation. Finally, chronic, reproductive, and juvenile toxicology studies using the RM-493-mPEG-DSPE formulation have been completed.

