### **8.6.1. Definition of Adverse Events**

#### **8.6.1.1. Adverse Event (AE)**

An AE is defined as any untoward medical occurrence associated with the use of a drug in humans, whether or not it is considered drug related. Patients/caregivers will be instructed to contact the Investigator at any time after a patient has been enrolled, before treatment, during treatment, or within 30 days following the cessation of treatment, if any symptoms develop.

A TEAE is defined as any event not present before exposure to trial drug or any event already present that worsens in intensity or frequency after exposure.

A suspected adverse reaction is any AE for which there is a reasonable possibility that the trial drug caused the AE. For the purposes of investigational new drug safety reporting, "reasonable possibility" means that there is evidence to suggest a causal relationship between the trial drug and the AE. A suspected adverse reaction implies a lesser degree of certainty about causality than an adverse reaction.

An adverse reaction is any AE caused by a trial drug. Adverse reactions belong to a subset of all suspected adverse reactions and indicate that there are reasons to conclude that the trial drug caused the event.

An AE or suspected adverse reaction is considered "unexpected" if it is not listed in the Reference Safety Information section of the Investigator brochure or if it occurs with specificity or severity that has not been previously observed with the trial drug being tested; or, if an Investigator brochure is not required or available, the AE or suspected adverse reaction is not consistent with the risk information described in the general investigational plan or elsewhere in

the current application. For example, under this definition, hepatic necrosis would be unexpected (by virtue of greater severity) if the IB referred only to elevated hepatic enzymes or hepatitis. Similarly, cerebral thromboembolism and cerebral vasculitis would be unexpected (by virtue of greater specificity) if the IB listed only cerebral vascular accidents. “Unexpected,” as used in this definition, also refers to AEs or suspected adverse reactions that are mentioned in the IB as occurring with a class of drugs or as anticipated from the pharmacological properties of the drug but are not specifically mentioned as occurring with the particular drug under investigation.

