### **3.5.3 Physical Examination**

A complete physical examination will be conducted at screening and at the EOT Visit. At other timepoints, an abbreviated examination will be performed. The abbreviated examination should focus on heart, lungs, skin, neurologic exam, and any areas of previous abnormal findings, noting any changes from baseline. Tanner staging should be performed at Screening and at the EOT (Week 52) visit. It may be done at additional visits, at the discretion of the PI. While the findings from the physical examination will not be captured on the eCRF, nor analyzed directly, changes from baseline in any physical examination findings identified by the Investigator as clinically significant (CS) will be recorded as an adverse event (AE).

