### **10.3 Adverse Events**

An AE is any untoward medical occurrence in a patient or clinical study patient, temporally associated with the use of study treatment, whether or not considered related to the study treatment. An AE can therefore be any unfavorable and unintended sign (including an abnormal laboratory finding), symptom, or disease (new or exacerbated) temporally associated with the use of study treatment. AEs, including Serious Adverse Events (SAE), will be collected from the provision of informed consent until the EOS visit. All AEs reported will be coded using the MedDRA version in force at the time of database freeze) and classified by MedDRA SOC and PT. The MedDRA version used for the coding will be noted as a footnote in the tables and listings.

All AEs will be presented by patient in a data listing. The listing will show the verbatim term, MedDRA SOC, MedDRA PT, event start date, event end date (or ongoing), SAE indicator, severity, relationship to study drug, action taken with study drug, action taken, and outcome.

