## 10.5 Vital Signs

The aggregated vital signs (described in [Section 3.5.1](#) and [3.5.2](#)) at each study visit and the changes from baseline to any post-baseline visit will be summarized using descriptive statistics.

Vital signs will be presented in a listing. The listing will show the assessment date, vital sign, indicator measurement was not done (if applicable), measurement value, and the change from baseline. Values will include both the triplicate measurements and their aggregated value, where applicable.

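### Protocol 8.6.4 makes AE recording optional for clinically significant laboratory, BP and pulse changes, at odds with the AE definitions, so non-serious TEAE counts for these events can be incomplete and vary by site

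*Protocol*

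**What the plan says.** Protocol 8.6.4 (Recording Adverse Events) says: "Clinically significant changes in laboratory values, BP, and pulse need not be reported as AEs". The next sentence sets the limit: "However, abnormal values that constitute an SAE or lead to discontinuation of administration of trial drug must be reported and recorded as an AE".

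Other parts of the plan define and collect AEs more broadly:

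- Protocol 8.6.1.1: "An AE is defined as any untoward medical occurrence associated with the use of a drug in humans". The same section requires every AE from enrollment to 30 days after treatment to be recorded, and Protocol 8.6.5 sends every reported or observed AE to the AE page of the eCRF. Neither exempts laboratory values, BP or pulse.
- SAP 10.3: "An AE can therefore be any unfavorable and unintended sign (including an abnormal laboratory finding), symptom, or disease (new or exacerbated").
- SAP 3.5.3 provides that changes from baseline in "physical examination findings identified by the Investigator as clinically significant (CS) will be recorded as an adverse event (AE").

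These data are also reported outside the AE tables. SAP 10.4 classes out-of-range laboratory values as clinically significant or not and tabulates shifts with patient counts. For vital signs, SAP 10.5 says that aggregated values "at each study visit and the changes from baseline to any post-baseline visit will be summarized using descriptive statistics", and adds a patient listing. The table of changes from the protocol in SAP 16.2, as extracted, has no entry on this point.

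**The concern.** Frequency and severity of AEs is a secondary endpoint (Protocol Table 2). The TEAE tables can count only what sites enter on the AE page. If one passage lets an investigator leave out a clinically significant change and others call for its entry, the count depends on which passage the site follows.

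Recording as an AE also triggers the causality judgement (Protocol 8.6.2), the intensity grade (8.6.4) and follow-up (8.6.5). A change that is not recorded receives none of these.

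BP and pulse are the weakest point because no other output carries a clinical-significance flag for vital signs. The protocol treats them as worth watching: Section 3.2 reports that in obese monkeys "setmelanotide did not increase blood pressure (BP) or heart rate (HR), a potential concern observed with other MC4R agonist compounds", and Section 8.3.1 provides for repeat measures when BP or heart rate rises significantly.

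**Working it through.** The documents state no TEAE rate and no power-based sample size, so there is no figure of the plan's own to reproduce. The check sets the passages side by side, then illustrates the size.

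**Step 1: how a non-serious, clinically significant change that does not stop treatment is handled**

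| Type of finding | Protocol 8.6.4 | Protocol 8.6.1.1 and 8.6.5 | SAP AE text | Other SAP output |
|---|---|---|---|---|
| Laboratory value | AE optional | AE if untoward; all AEs recorded | Can be an AE (10.3) | Significance classes, shift tables, listing (10.4) |
| BP, pulse | AE optional | AE if untoward; all AEs recorded | Not named; could fall under an unfavorable sign (10.3) | Descriptive statistics and listing, no significance class (10.5) |
| Physical examination finding | No carve-out | AE if untoward; all AEs recorded | Recorded as AE (3.5.3) | Not captured on the eCRF as such |

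So a clinically significant examination finding is an AE, while a clinically significant BP rise in the same child at the same visit is optional.

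The exception in 8.6.4 covers SAEs and discontinuation only. A change that leads to a paused escalation or a dose reduction (Protocol 7.3) falls outside it. Protocol 7.4 allows new concomitant medication only to treat an AE, which sits awkwardly with a change that need not be an AE. These passages must be reconciled too.

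**Step 2: weight of one patient**

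The planned enrollment is about 10 to 15 (Protocol 9.1). SAP 10.3.2 counts each patient at most once per category, so one patient is worth 100/N points:

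- N = 10: 100/10 = 10.0
- N = 12: 100/12 = 8.3
- N = 15: 100/15 = 6.7

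**Step 3: possible shortfall (assumed inputs; the documents give none of them)**

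Let c be the share of patients with such a change, w the share of these changes left unrecorded, and q the share of patients with some other recorded TEAE, independent of c.

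- Shortfall in a category grouping these events = w × c
- Shortfall in the rate of any TEAE = w × c × (1 − q)

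| w | c | q | Event category (points) | Any TEAE (points) |
|---|---|---|---|---|
| 0 | 10–30% | 80–100% | 0 | 0 |
| 0.5 | 20% | 80% | 10 | 2 |
| 1 | 10% | 95% | 10 | 0.5 |
| 1 | 30% | 80% | 30 | 6 |
| 1 | 30% | 100% | 30 | 0 |

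Over the whole range the shortfall is 0 to 30 points in the event category and 0 to 6 points in the any-TEAE rate. If the events spread over several preferred terms, each term loses less.

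**Step 4: chance that the question arises at all**

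P(at least one such patient) = 1 − (1 − c)^N:

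- c = 10%: 0.651 at N = 10; 0.794 at N = 15
- c = 20%: 0.893 and 0.965
- c = 30%: 0.972 and 0.995

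Under these assumed risks, the trial would more likely than not contain at least one affected child.

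**The case against.** The strongest reply is that little is lost, because the data are reported elsewhere. Much of this stands. Laboratory changes keep their significance class and patient counts in SAP 10.4. Heart rate and the overall interpretation from the ECG are tabulated under SAP 10.6. Vital signs and laboratory evaluations are secondary endpoints in their own right.

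A reader might infer that a BP rise disappears into a mean: an assumed 15 mmHg rise in one of 12 children moves the mean by only 15/12 = 1.25 mmHg. The documents do not support that inference. SAP Section 4 defines descriptive statistics to include the SD, median, minimum and maximum, so the largest change at a visit is printed. SAP 10.5 also lists each child's values and change from baseline, and a listing of 10 to 15 children can be read in full. What is missing is narrower: a count of clinically significant BP and pulse changes, and any causality or severity judgement unless the change is recorded as an AE.

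A reader might also infer that sites are told not to report, so that TEAE rates will be understated. The wording permits omission without ordering it, and the shortfall is zero if investigators record these changes anyway. Nor does SAP 10.3 make every abnormal laboratory finding an AE: it says that one can be, and it does not name BP or pulse. Protocol 3.2 should not be read as a BP signal for setmelanotide; the concern there was with other compounds.

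The last objection is timing. Protocol Version 5.0 is dated 22 June 2023, the interim analysis is set for 23 August 2023 (SAP 12), and the estimated last completion is September 2023. A new sentence alone would not recover earlier events and would leave two recording regimes. This stands and shapes the fix.

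**Conclusion.** The inconsistency is real and should be corrected. Protocol 8.6.4 cannot be squared with Protocol 8.6.1.1 and 8.6.5, and it differs from the approach in SAP 10.3 and 3.5.3. Against the broader definition, any error in the counts is toward too few events. Counts of non-serious TEAEs for laboratory, BP and pulse changes can be incomplete and can differ between sites. The exception in 8.6.4 keeps serious TEAEs and TEAEs leading to drug discontinuation out of the problem.

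The firm figure is the weight of one patient, 6.7 to 10.0 points. It falls mainly on specific laboratory, BP or pulse terms, because the any-TEAE rate changes only for a child with no other recorded TEAE. The actual shortfall is unknown: the ranges shown rest entirely on assumed values of c, q and w. The practical gap is larger for BP and pulse than for laboratory values.

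**What to change.** Preferred: amend Protocol 8.6.4 so that one rule applies. Suggested wording: *Changes in laboratory values, BP or pulse that the Investigator judges clinically significant are recorded as AEs; changes judged not clinically significant need not be.* This fits Protocol 8.6.1.1 and 8.6.5, applies to these measurements the threshold that SAP 3.5.3 uses for examination findings, and is compatible with SAP 10.3, which sets no threshold of its own.

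If the carve-out is intended: state it in SAP 10.3, log it in SAP 16.2, and add to SAP 10.5 a patient-level count of clinically significant BP and pulse changes as judged by the Investigator.

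Under either option, review laboratory, BP and pulse values already collected so that the same rule covers the whole trial, and say in the study report that this was done.

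Cost: a one-sentence protocol change or a short SAP addition, somewhat more AE entries, a slightly less favorable AE table, and the retrospective review, which is limited to about 10 to 15 patients.

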### 8.6.5. Reporting Adverse Events

All AEs reported or observed during the trial will be recorded on the AE page of the eCRF. Information to be collected includes drug treatment, type of event, time of onset, dosage, Investigator-specified assessment of severity and relationship to trial drug, time of resolution of the event, seriousness, any required treatment or evaluations, and outcome. Any AEs resulting from concurrent illnesses, reactions to concurrent illnesses, reactions to concurrent medications, or progression of disease states must also be reported. All AEs will be followed until they are resolved, stable, or judged by the Investigator to be not clinically significant. The MedDRA will be used to code all AEs. Any medical condition that is present at the time that the subject is screened but does not deteriorate should not be reported as an AE. However, if it deteriorates at any time during the trial, it should be recorded as an AE.

A referral to a mental health practitioner should be issued to the patient for any instance of reported AEs indicative of a change in mental health status.

#### **8.6.6. Reporting of Expedited Safety Observations by the Investigator**

Any occurrence of the following events or outcomes in a subject in the trial must be reported expeditiously by the Investigator or qualified designee to the Sponsor via an SAE form:

- SAE
- Death of a subject
- Overdose
- Cancer

The Investigator is to report any of the items in the list above within 24 hours of becoming aware of the event. Any observation reported to The Sponsor that is also an AE, is to be recorded in the eCRF, as well as in the subject's source documentation along with any actions taken. If not all information is available at the time of the initial report, follow-up SAE reports will be completed and submitted. The Investigator is required to follow SAEs until resolution regardless of whether the patients are still participating in the trial. Resolution is defined as follows:

- Resolved with or without residual effects
- A return to baseline for a pre-existing condition
- The Investigator does not expect any further improvement or worsening of the event
- Fatal outcome -If an autopsy is performed on a deceased subject, the autopsy report must be provided to the Sponsor as soon as it is available.

## 9. STATISTICS

Details of all statistical analyses will be described in a separate Statistical Analysis Plan (SAP).

### 9.1. Sample Size Determination

No formal sample size determination was made based on statistical inference. The sample size is not driven by statistical power considerations but is primarily driven by clinical and practical considerations. Given the rare patient population, the trial plans to enroll approximately 10-15 patients (approximately 5 or more pediatric patients with biallelic mutations of the *POMC*, *PCSK1* or *LEPR* genes and approximately 5 or more pediatric patients with BBS).

### 9.2. Statistical Analyses

The primary objective is to evaluate the effect of setmelanotide on weight-related parameters measured in terms of the response rate to setmelanotide. Due to the small sample size of the trial, no statistical hypothesis testing is planned, and efficacy will be reported using descriptive statistics. The safety population, including all patients who receive at least 1 dose of setmelanotide, will be used as the primary analysis population for all the analyses.

AEs will be coded by preferred term (PT) and system organ class (SOC) using the latest version of MedDRA and summarized. All AE data will be presented in a data listing. TEAEs will be summarized, including by severity and relationship to trial drug. Serious AEs and AEs leading to early discontinuation will also be presented in data listings.

Actual values and changes from baseline for clinical laboratory test results, vital sign measurements etc. will be summarized using descriptive statistics (N, mean, standard deviation, median, minimum, and maximum). Shift tables will be generated for clinical laboratory test results. Clinical laboratory test results, vital sign measurements etc. will be presented in data listings.

The secondary objectives are to evaluate the effect of setmelanotide on additional weight-related parameters, as well as safety and tolerability. [REDACTED]

[REDACTED] No statistical hypothesis was made. The collected parameters will be summarized with appropriate descriptive statistics.

Due to the small sample size, summary statistics by genotype may be provided as appropriate.

## **10. DIRECT ACCESS TO SOURCE DATA/DOCUMENTS**

### **10.1. Trial Monitoring**

During the trial, a monitor from The Sponsor or designee will have regular contacts with the investigational site, for the following:

- Provide information and support to the Investigator(s) and site staff
- Confirm that facilities remain acceptable
- Confirm that the investigational team is adhering to the protocol, that data are being accurately recorded in the case report forms, and that investigational product accountability checks are being performed
- Perform source data verification. This includes a comparison of the data in the case report forms with the patient's medical records at the hospital or practice, and other records relevant to the trial. This will require direct access to all original records for each patient (e.g., clinic charts).
- Record and report any protocol deviations not previously sent to The Sponsor
- Confirm AEs and SAEs have been properly documented on eCRFs and confirm any SAEs have been forwarded to The Sponsor and those SAEs that met criteria for reporting have been forwarded to the IRB.

The monitor will be available between monitoring visits if the Investigator(s) or other staff needs information or advice.

#### **10.1.1. Trial Conduct During the COVID-19 Pandemic**

The worldwide Coronavirus Disease 2019 (COVID-19) pandemic may impact the conduct of clinical trials due to the challenges from quarantines, site closures, travel limitations, and other considerations if site personnel or patients become potentially exposed to or infected with COVID-19. To assure the safety of patients, maintain compliance with GCP, and minimize risks to trial integrity, if necessary, in consultation with the Sponsor, the method of assessment may be changed (e.g., paper assessments replaced by electronic assessments). In addition, site visits may be replaced with telephone, internet-based video-conferencing applications, or home visits by qualified health care professionals. Normal procedures, as detailed in this protocol, will be resumed as soon as possible thereafter.

More detailed guidance on trial conduct during the COVID-19 pandemic is provided in [Appendix 2](#).

